### 9.2 Sample Size and Accrual

The primary aim of the study is to assess the local and systemic safety of a single dose of placebo vaginal film. The primary endpoint is the proportion of participants who experience a Grade 2 or higher adverse event. The proposed total sample size is N=64 divided into 4 arms (placebo film with follow up at days 3, 7, 10, or 14 assigned at a 1:1:1:1 ratio). Based on previous studies of vaginal products conducted at the study site, the accrual of 64 eligible subjects with normal reproductive tracts is expected to require the screening of approximately 150 volunteers. Since unevaluable participants will be replaced, it is anticipated that 64 women exposed to study product will complete study visit 3.

The sample size is based on the exact binomial probability of observing at least two Grade 2 or higher Adverse Events. For a given arm, if the true rate of a given toxicity endpoint is 5%, 16 women per arm provide 80% power to exclude toxicity endpoint rates greater than 27% (the probability of observing zero or one event is less than 0.05 when the true rate is 27%).

Table 6: Power Calculations for FAME 101

Event Rate	P(No events   n=16)	P(1 or more events   n=16)	P(2 or more events   n=16)
1%	0.851	0.149	0.011
5%	0.440	0.560	0.189
10%	0.185	0.815	0.485
15%	0.074	0.926	0.716
20%	0.028	0.972	0.859
25%	0.010	0.990	0.937
27%	0.007	0.993	0.955
30%	0.003	0.997	0.974
35%	0.001	0.999	0.990

In previous studies of two different placebo film products the combined frequency of Grade 2 or higher Adverse Events was 19%. Assuming a similar frequency in the current study, a sample size of 64 women will assure that a 95% confidence interval for the Grade 2 or higher Adverse Events rate has an upper limit of no greater than 30%.

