#### *Quantitative vaginal cultures and quantitative PCR*

Meaningful changes will be defined by greater than or equal to 1 log changes in dominant members of the microbiota, including *Lactobacillus* species, *Gardnerella vaginalis*, key anaerobic microorganisms, *Enterococcus* species, *Escherichia coli*, *Staphylococcus aureus*, Group B *Streptococcus*, and *Candida* species.

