### **9.6.3 Secondary and Exploratory Endpoint Analysis**

Summary statistics of frequencies, percentages, and 95% confidence intervals will be provided for categorical data. Means, standard deviations, medians, ranges and 95% confidence

intervals will be provided for continuous data. Methods for the analyses of the secondary endpoints are described below.

One-way analysis of variance (ANOVA) and Kruskal-Wallis tests will be used, where appropriate, to evaluate differences in the following continuous variables between the study arms: levels of glycoproteins and mucins in CVL, levels of cytokines and innate immunity factors, and antiviral activity in CVL. Between groups, pre- to post-exposure changes in the above endpoints will also be evaluated using ANOVA and Kruskal-Wallis tests, where appropriate, while paired Student's t- and Wilcoxon signed-rank tests will be used to evaluate these changes within each study arm. Mixed effects linear regression will be used to evaluate associations between days of exposure to study product and these outcomes.

Nugent score will be categorized as follows: normal (score 0-3), intermediate (score 4-6), and bacterial vaginosis (score 7-10). Differences in the categorized Nugent score pre and post exposure levels will be evaluated using Fisher's exact, while McNemar's tests will be used to evaluate pre- to post-exposure shifts between normal (score 0-3) and abnormal (score 4-10) vaginal microflora within each study arm.

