Prevalence of microorganisms at each visit will be compared between the study arms using Fisher's exact tests, while pre- to post-exposure shifts will be evaluated within each group using McNemar's tests. Differences between the study arms in the quantity of microorganisms at each visit, as well as the change in quantity, will be evaluated using Mann-Whitney U tests. Meaningful changes will be defined by greater than or equal to 1 log changes in dominant members of the microflora, including Lactobacillus (H2O2 positive and negative strains), anaerobic gram negative rods, Gardnerella vaginalis, Candida species, facultative gram negative rods, Streptococci and facultative gram positive cocci and rods. Fisher's exact tests will be used to evaluate differences in these changes between study arms. Mixed effects linear regression (for continuous outcomes) and generalized estimating equations (for binary outcomes) will be used to evaluate associations between days of exposure to study product and these outcomes.

Time since last menstrual period will be included as a potential confounder in these analyses.

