**Table 7: Statistical Analysis Plan**

Endpoint	Variable	Statistics
Primary	Adverse Events	Frequency, Percent, 95% Confidence Interval
Exploratory	Persistence of Eudragit® in CVL	Frequency, Percent, 95% Confidence Interval
	Levels of glycoproteins and mucins, in CVL	Mean, SD, Median, Range, 95% Confidence Interval
	Antiviral activity in CVL	Mean, SD, Median, Range, 95% Confidence Interval

	Change in vaginal flora (Nugent score)	Frequency, Percent, 95% Confidence Interval
	Culture/qPCR results from vaginal organisms	Frequency, Percent, 95% Confidence Interval
	Change in cytokine and innate immunity factors	Mean, SD, Median, Range, 95% Confidence Interval
	Lectin Microarray to assess changes in glycome	Mean, SD, Median, Range, 95% Confidence Interval

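### The only named within-arm before/after test for vaginal organisms uses detected/not detected, so a 1-log fall in a dominant organism leaves it almost nothing to count

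*Combined protocol and SAP*

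**What the plan says.** Section 3.3 sets an exploratory objective of comparing the vaginal microbiota before and after film use. Section 9.3.2 (Vaginal Microenvironment) explains that, with no film-free arm, each woman is her own control. Under quantitative cultures and PCR it adds: "Meaningful changes will be defined by greater than or equal to 1 log changes in dominant members of the microbiota".

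Section 9.6.3 then assigns the tests for organisms:

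- **Prevalence:** Fisher's exact test between arms, "while pre- to post-exposure shifts will be evaluated within each group using McNemar's tests".
- **Quantity:** "Differences between the study arms in the quantity of microorganisms at each visit, as well as the change in quantity, will be evaluated" by Mann-Whitney U.
- **The 1-log change:** Fisher's exact test, again between arms.
- **Wear time:** mixed effects linear regression for continuous outcomes and generalized estimating equations for binary ones, on days of exposure.

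For the continuous lavage (CVL) measures, the same section names paired t-tests and says "Wilcoxon signed-rank tests will be used to evaluate these changes within each study arm". Table 7 has one row, "Culture/qPCR results from vaginal organisms", summarised by frequency, percent and 95% confidence interval. On size, section 9.2 says: "The proposed total sample size is N=64 divided into 4 arms", which is 16 women per arm.

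**The concern.** The before/after contrast within women is what answers the microbiota objective. The paired test named for it works on prevalence, while the plan's criterion for a change that matters is on the log scale. An organism can lose nine tenths of its quantity and still be detected, in which case the woman is a concordant pair and adds nothing to McNemar's test.

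The tests that do use quantity compare arms that differ only in when Visit 3 takes place. They have power when the change grows with wear time. If the film lowers lactobacilli by a similar amount in every arm, there is no difference between arms to find. The plan gives no reason for treating organism quantities differently from the lavage measures. The risk is a statement of no within-arm shift in flora that rests on a test unable to see the shift the plan calls meaningful.

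**Working it through.** **The plan's own figure.** Section 9.2 gives 80% power at 16 women per arm, with zero or one event at a true rate of 5%, to exclude rates above 27%. Exact binomial: 0.95^16 + 16 × 0.05 × 0.95^15 = 0.440 + 0.371 = 0.811. At 27%: 0.73^16 + 16 × 0.27 × 0.73^15 = 0.0065 + 0.0385 = 0.045. Both agree with the text. The plan states no power for the flora tests, so there is no figure to reproduce on this point.

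**What McNemar needs.** With k discordant women, all in one direction, the exact two-sided p is 2 × 0.5^k. For k = 5 this is 0.0625 and for k = 6 it is 0.031. So at least 6 of the 16 women must change detection status, all the same way. Two-sided 0.05 is an assumption, since the plan states no level for these tests.

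**Expected discordant pairs.** The documents give no quantities, detection limits or SDs. Assumed: baseline mean 7 log10 with SD 1, detection limit 3 log10, a true mean fall of 1 log, and SD of within-woman change 1.0 or 1.5. The follow-up value then has mean 6 and SD √(1 + SD²).

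- SD 1.0: P(undetected) = Φ(−3/1.414) = 0.017, and 16 × 0.017 = 0.27 women expected.
- SD 1.5: P(undetected) = Φ(−3/1.803) = 0.048, and 16 × 0.048 = 0.77 women expected. The chance of exactly six is about 8008 × 0.048^6 × 0.952^10 = 0.00006.

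**Power by simulation** (16 women, 1,500 runs per setting; the two figures are for SD of change 1.0 / 1.5):

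| Baseline mean, limit (log10) | McNemar on detection | Signed-rank on log10 |
|---|---|---|
| 7, limit 2 | 0% / 0% | 96% / 66% |
| 7, limit 3 | 0% / 0% | 94% / 67% |
| 6, limit 3 | 0% / 1% | 95% / 67% |
| 5, limit 3 | 11% / 25% | 93% / 62% |
| 4, limit 3 | 47% / 45% | 84% / 42% |

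The last row is sensitive to the assumed spread between women. Other reasonable choices put McNemar anywhere from 11% to 54% there. Pooling all 64 women does not rescue McNemar at a baseline of 7 (0% to 8%).

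**Between-arm tests.** With the same 1-log step in every arm, a four-arm Kruskal-Wallis test on change (standing in for Mann-Whitney, which compares two groups) rejected in 4% to 6% of 300 runs. Mann-Whitney of day 3 against day 14 rejected in 4%. Both are about the nominal error rate.

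**The mixed model.** With 64 women, Visit 2 as day 0 and Visit 3 at its scheduled day, it rejected in 100% of runs for the common step and about 5% with no effect. With post-exposure data alone it rejects at about the nominal level. Even when it detects the step, it describes it as a slope. The within-woman least-squares slope for a uniform −1 log is −(3+7+10+14)/(9+49+100+196) = −34/354 = −0.096 log per day. That implies −0.29 log at day 3 and −1.34 at day 14, where the truth is −1 at both.

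**An illustration in the protocol.** In the Appendix IV macaque raw data, H2O2-positive lactobacilli are present in 6 of 7 animals on both days, with no discordant animal. Yet 4 of the 7 semi-quantitative scores changed: one fell from 4 to 1 and three rose. These are growth scores, not log10 counts, so they show the mechanism only.

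**The case against.** The strongest reply is that the plan is not blind to quantity. A reader might infer that McNemar is the only within-woman analysis. It is not: a mixed model implies repeated measures per woman, flora is sampled at Visits 2, 3 and 4 (Tables 3 to 5), and nothing says Visit 2 is left out. With Visit 2 as day 0 the model would find a common fall. This stands. What remains is that the plan does not specify it, and that a per-day slope pooled over arms is not a before/after change within arm.

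A reader might also infer that a tenfold fall would be reported as unchanged percentages. The documents do not support that either. Section 9.6.3 opens by promising means, medians and confidence intervals for continuous data, so quantities at each visit should be described. Table 7 does not limit its frequencies to detection, and they could count 1-log changes. With a mean fall of 1 log, half the women would fall by at least 1 log, against Φ(−1) = 16% (SD 1.0) or Φ(−0.667) = 25% (SD 1.5) with no effect. But no summary of paired change is named, and rises and falls are not said to be separated.

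McNemar also does its proper job for organisms near the detection limit, and it counts complete loss. In the last row of the table, at SD 1.5, it is as good as the signed-rank test.

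**Conclusion.** The point holds in a limited form. For culture and qPCR organisms, the only named within-arm before/after test ignores quantity, and the 1-log criterion is tested only between arms given the same film. For a dominant organism well above the detection limit, a true 1-log fall gives McNemar near-zero power at 16 women, against about 65% to 95% for a signed-rank test.

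Those powers rest on assumed means, detection limits and SDs of change. The mechanism needs only that the organism stays detectable after the fall. It does not extend to organisms near the limit or to complete loss. Whether the mixed model closes the gap depends on a detail the plan leaves open. The endpoint is exploratory and the primary safety conclusion does not depend on it, so this is an inexpensive improvement and not a flaw in the trial's main result.

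**What to change.** - In section 9.6.3, add a paired Wilcoxon signed-rank test on log10 quantity from Visit 2 to Visit 3 for each organism, within arm and pooled over arms, with non-detects set at the assay's detection limit. This matches what the section already does for the lavage measures.
- In Table 7, report the median log10 change with a 95% confidence interval, and the numbers of women with a rise and with a fall of at least 1 log, separately.
- Keep McNemar on prevalence for organisms often undetected at baseline.
- State that Visit 2 enters the mixed model as day 0.

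The cost is a few lines of analysis-plan wording and an extra summary column, with no new samples or visits. The downsides are a few more exploratory p-values and ties at the detection limit for rarely detected organisms.

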## **4.5 Study Groups**

All participants will receive a single dose of the vaginal film. They will be randomized at enrollment to the timing of Visit 3. In total, there will be four groups:

- Visit 3 at Day 3 (range days 2-4)
- Visit 3 at Day 7 (range days 6-8)
- Visit 3 at Day 10 (range days 9-11)
- Visit 3 at Day 14 (range days 12-16)

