### 7.3 Visit 2: Enrollment

Subjects who meet the inclusion and exclusion criteria following the Screening Visit may schedule an Enrollment Visit. Care will be taken to schedule the Enrollment visit at a time when the participant is not expecting to be actively bleeding or anticipating her menses within 14 days.

Before performing any enrollment procedures, study staff will confirm eligibility. The participant will undergo a pelvic examination. Pelvic specimens as described below will be collected and the study staff will assess for bleeding. If no bleeding or other exclusionary findings are evident, the participant will then be randomized to the timing of Visit 3. The act of randomization is considered the act of enrollment for this study. Subjects with menses like vaginal bleeding at the Enrollment visit will not be randomized/enrolled at that time. These subjects may be rescheduled if vaginal bleeding resolves before 45 days from Screening have elapsed. If vaginal

bleeding does not resolve during the window period, and the subject expresses interest in enrollment for the study, she may be offered a rescreening attempt.

After eligibility is confirmed, the clinician will go to the Pharmacy to obtain the study product. Participants will be counselled thoroughly on product administration and then handed the film in its packaging. The participant will attempt to insert the film while a site staff member stands behind a curtain to maintain privacy. Should the participant have any concerns or questions, the site staff member will be readily available. Immediately after the participant attempts insertion, the site clinician will do a quick inspection of the external genitalia to assess for proper placement. If the majority of the film is visible outside of the vaginal introitus, the clinician will return to the pharmacy to retrieve a second dose of the vaginal film. The clinician will then remove visible film, insert a speculum, remove visible film from inside the vagina, and place a second film in the proximal third of the vagina using a forceps instrument. After film placement, participants will be scheduled for Visit 3. When Visit 3 occurs will be determined by randomization (3, 7, 10 or 14 days).

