### **9.5 Random Assignment**

The randomization scheme will be generated and maintained by a member of the Data Management Division at the study site. Women will be randomized to one of the four arms at a 1:1:1:1 ratio using a permuted block design with random block sizes of 4 and 8. In order to minimize bias in group assignment, participants will be given study identification numbers. A study staff member will allot the identification numbers in sequential order as participants become eligible to enroll in the study. These numbers will be randomly assigned with timing of Visit 3. The randomization scheme will be created for a total of 72 participants; the overage will be created to compensate for participant withdrawals or unusable products.

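### Section 9.6.3 assigns the two-sample Mann-Whitney U test to a comparison of microorganism quantity across four randomized arms, without naming pairs, a reference arm or an adjustment (minor; exploratory endpoint)

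*Combined protocol and SAP*

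**What the plan says.** Four arms are fixed throughout the document. Section 4.5 states "In total, there will be four groups", defined by a Visit 3 at day 3, 7, 10 or 14. Section 9.5 states "Women will be randomized to one of the four arms at a 1:1:1:1 ratio". Section 9.2 divides 64 women into four arms and states that "16 women per arm provide 80% power" for the safety endpoint. Every arm receives the same single placebo film, so none is a control.

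Section 9.6.3 treats two groups of continuous outcomes differently:

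- **CVL outcomes.** One-way ANOVA or Kruskal-Wallis is planned for "differences in the following continuous variables between the study arms: levels of glycoproteins and mucins in CVL, levels of cytokines and innate immunity factors", and for antiviral activity. The same tests are planned between groups for the pre- to post-exposure changes in these outcomes.
- **Microorganism quantity.** Between-arm differences in "the quantity of microorganisms at each visit, as well as the change in quantity, will be evaluated using Mann-Whitney U tests". No pairs, reference arm, overall k-sample test or multiplicity rule follows.

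The same part of section 9.6.3 contains two neighbouring analyses. For changes of at least 1 log, Fisher's "exact tests will be used to evaluate differences in these changes between study arms". Mixed effects linear regression (continuous outcomes) and generalized estimating equations (binary outcomes) relate the outcomes to days of exposure. The next sentence reads "Time since last menstrual period will be included as a potential confounder in these analyses".

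**The concern.** A Mann-Whitney U test takes exactly two samples. With four arms there are six possible pairs, and the design does not point to any of them: with no control arm, day 3 is no more natural a reference than day 14. The sentence therefore does not define an analysis. An analyst could run all six pairs, compare three arms with a chosen fourth, or pool arms into two groups, and each choice would fit the text.

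At stake are the reproducibility of one exploratory analysis and its false-positive rate. If the choice is made after the data are seen, or all pairs are run unadjusted, an apparent effect on the microbiota at one follow-up time could be reported more often than a nominal 5% level suggests. Section 9.6.3 already uses a k-sample test for the same kind of comparison elsewhere, so this looks like an oversight rather than a deliberate choice.

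**Working it through.** **Inputs.** Four arms at 1:1:1:1 and N = 64 (sections 9.2 and 9.5), so 64 / 4 = 16 per arm. The plan states no significance level for this analysis. A two-sided 5% level per test is assumed here, with no true difference between arms.

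**The plan's own figure for 16 per arm.** It concerns the primary safety endpoint, and it reproduces.

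- True rate 5%: P(0 or 1 event) = 0.95^16 + 16 × 0.05 × 0.95^15 = 0.440 + 0.371 = 0.811 (plan: 80%).
- True rate 27%: P(0 or 1 event) = 0.73^16 + 16 × 0.27 × 0.73^15 = 0.0065 + 0.0385 = 0.045 (plan: below 0.05).

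The arm size is therefore sound for its purpose. The plan gives no operating figure for the Mann-Whitney analysis.

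**Number of comparisons.** All pairs: C(4,2) = 4 × 3 / 2 = 6. Against one reference arm: 3. One Kruskal-Wallis test: 1.

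**Rough figure if the tests were independent.** Six pairs: 1 − 0.95^6 = 0.265. Three pairs: 1 − 0.95^3 = 0.143. These overstate the error, because pairs share arms and are correlated, so the error was simulated.

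**Simulation under no difference.** 100,000 trials, four arms of 16 from one normal distribution. Mann-Whitney was exact and two-sided, rejecting when the smaller U is 75 or less (attained size 0.0468). Kruskal-Wallis was referred to chi-square with 3 degrees of freedom.

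| Way of carrying out the comparison | Chance of at least one false positive, per organism and comparison |
|---|---|
| One pre-named pair | 0.047 |
| Three pairs against one reference arm, unadjusted | 0.118 (SE 0.0010) |
| All six pairs, unadjusted | 0.195 (SE 0.0013) |
| All six pairs, Holm-adjusted | 0.038 |
| One Kruskal-Wallis test | 0.047 (SE 0.0007) |

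A separate run of 40,000 trials gave 0.194 (six pairs), 0.119 (three pairs) and 0.046 (Kruskal-Wallis).

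**Sensitivity to ties.** Culture and PCR quantities may include many non-detects. With an assumed 30% or 60% non-detects (20,000 trials each, tie-corrected tests), any of six pairs gave 0.197 and 0.185, and Kruskal-Wallis gave 0.050 and 0.046. The contrast does not depend on the normal model.

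**The case against.** The strongest reply is that the data are already analysed across all arms. The mixed effects regression on days of exposure uses every arm and the 3, 7, 10 and 14 day order, and it can cover quantity as a continuous outcome. Fisher's exact test between arms covers changes of at least 1 log, which is the plan's own definition of a meaningful change. This stands, and it limits the consequence: a reader should not infer that the plan lacks any all-arm analysis of the microbiota. It does not remove the defect, because the regression tests an association with days of exposure and the Fisher test uses a dichotomized change. Neither says which arms the Mann-Whitney test compares.

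A second reply is that the plural *tests* implies pairwise comparisons. It may equally reflect several organisms and visits. If pairs are meant, which ones and with what adjustment remain unstated.

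Other stronger readings do not hold:

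- **Covariate.** A reader might infer that the plan requires a rank test to adjust for time since the last menses, which it cannot do. The sentence directly follows the one on regression and estimating equations and most naturally refers to those models.
- **Visit 2.** A between-arm test at every visit includes Visit 2, where specimens are taken first and "If no bleeding or other exclusionary findings are evident, the participant will then be randomized to the timing of Visit 3" (section 7.3). Such a test is uninformative, but it biases no result.
- **Table 7.** Its culture/qPCR row lists only descriptive statistics, but so does every other row. This shows nothing particular to this endpoint.

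**Conclusion.** The named test does not fit the four-arm design and is wrong as written. The severity is minor: the endpoint is exploratory, the primary safety analysis and sample size are untouched, and the regression on days of exposure remains available.

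The size, about 19% against about 5% per organism and comparison, is conditional on a two-sided 5% level, 16 evaluable women in each arm, no true differences and unadjusted testing of all six pairs. The plan commits to neither that level nor those pairs, so 19% is what one permitted reading would give and not a property of the plan. With three comparisons against one reference arm it would be about 12%. The mismatch between test and design does not depend on either figure.

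A reader might also infer that a Kruskal-Wallis test would settle multiplicity over the many organisms and visits. It would not: it makes each four-arm comparison well defined and keeps its error near the chosen level. Multiplicity across organisms is a separate matter that this point does not quantify.

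**What to change.** Replace the Mann-Whitney sentence in section 9.6.3 with wording such as:

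> Between-arm differences in microorganism quantity at each visit, and in its change from Visit 2 to Visit 3 and from Visit 2 to Visit 4, will be evaluated across all four arms using Kruskal-Wallis tests; any follow-up pairwise Mann-Whitney U tests will be adjusted over the six pairs (for example, Holm).

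This uses a test the section already names and states which changes are compared. Leave the mixed effects and estimating-equation models as they are.

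Two wording changes are optional. First, describe Visit 2 values by arm instead of testing them, for both prevalence and quantity so that the two agree. Second, state that the adjustment for time since the last menses applies to the regression models.

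The cost is a text edit to one section. Data collection, sample size and the primary analysis do not change.
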